### 9.2 Duration of Response (modify as necessary)

Not applicable

### 9.3 Progression-Free Survival (if applicable)

Not applicable

### 9.4 Other Response Parameters

No further parameters.

## 10. Data Reporting / Regulatory Considerations

### 10.1 Data Collection

The data collection plan for this study is to utilize REDCap to capture all treatment, toxicity, efficacy, and adverse event data for all enrolled patients. To ensure maximum compliance, subjects will be prompted with a text message to their mobile phone. To ensure HIPAA compliance, text messages will only read as "A new survey is due." Participants will be informed of this prompting protocol beforehand. No PHI, or any details of medical therapy, will be revealed in the text message or in the surveys administered through REDCap (please see the survey attachment to review how each survey will appear). Texts will be sent from a study dedicated phone controlled by the study staff. The study phone will be encrypted and managed by ITS per WCM regulation. Subjects will complete surveys at the following intervals: every 8 hours post-operative day 1 and 2, and every 12 hours post-operative day 3 through 7.

#### 10.1.1 REDCap

REDCap (Research Electronic Data Capture) is a free data management software system that is fully supported by the Weill-Cornell Medical Center CTSC. It is a tool

for the creation of customized, secure data management systems that include Web-based data-entry forms, reporting tools, and a full array of security features including user and group based privileges, authentication using institution LDAP system, with a full audit trail of data manipulation and export procedures. REDCap is maintained on CTSC-owned servers that are backed up nightly and support encrypted (SSL-based) connections. Nationally, the software is developed, enhanced and supported through a multi-institutional consortium led by the Vanderbilt University CTSA.

## **10.2 Regulatory Considerations**

All protocol amendments and consent form modifications will be made by the Principal Investigator. Pacira Pharmaceuticals, Inc. will have the opportunity to review and approve the changes prior to submission of these changes to the local IRB and distribution to participating sites.

## **11. Statistical Considerations (Statistical Analysis Plan)**

All investigator-initiated trials **must** include a study statistician assigned by the Division of Biostatistics and Epidemiology.

[name] has been assigned as the statistician.

## **11.1 Study Design/Endpoints**

The study will be a randomized double blind control trial. We will randomize into two arms: 25 patients in a control arm, and 25 patients in the intervention arm.

During the 7 subsequent post-op days participants in both the intervention and control arms will be asked to maintain the NRS-11 pain diary (0=no pain, 11=worst possible pain). Subjects will complete surveys at the following intervals: every 8 hours post-operative day 1 and 2, and every 12 hours post-operative day 3 through 7. The area under the curve will be computed using the linear trapezoidal rule to interpolate between survey responses, and assess overall pain burden over the time period.

Our primary endpoint is to compare the area-under-the-curve of the NRS-11 in days 1 and 2 ( $AUC_{days1-2}$ ). Average  $AUC_{days1-2}$  will be compared in treatment vs control

groups using a two-sample t-test allowing for unequal variances, with a two-sided alpha of 0.05. A 95% confidence interval for the difference in  $AUC_{days1-2}$  between arms will be estimated along with estimate and confidence intervals of average  $AUC_{days1-2}$  within each arm.

A secondary analysis will be the comparison of AUC in the first 60 hours ( $AUC_{60\_Hrs}$ ), followed by the full 7 days post-surgery ( $AUC_{days1-7}$ ), and similarly analyzed as the primary endpoint. Additional secondary analyses will include the percentage of patients who are opiate-free in days 1-7, the average number of narcotic tablets required at any time in days 1 through 7, and the time to first rescue narcotic utilization. Overall pain control satisfaction will be compared between the two arms (assessed on post-surgery day 7).

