## 1. Study Objectives

### 1.1 Primary Objectives

Our primary endpoint is the area-under-the-curve in the first 48 hours post-surgery for 11-point numerical pain rating scales (NRS-11) of patients who were injected with liposomal bupivacaine (mixed with standard bupivacaine) at the time of surgery against standard bupivacaine only.

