### 1.2 Secondary Objectives

Secondary endpoints:

Area-under-the-curve in the first 60 hours and 108 hours (7 days) post-surgery for 11-point numerical pain rating scales (NRS-11).

Average total number of narcotic tablets required between the intervention and control arms during post-operative day 1 through 7.

Time to first rescue narcotic utilization between the two arms.

Overall satisfaction of pain control regimen (ranked by the patients on post-operative day 7).

The percentage of patients remaining opiate free by post-operative day 7.

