### **5.4 Duration of Therapy and Criteria for Removal from Study**

- Not applicable – the study medication is administered once prior to wound closure during the surgery. Subjects may voluntarily withdrawal from the survey-portion of the study at anytime without consequences to their subsequent care.

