## **11.2 Sample Size/Accrual Rate**

The minimal clinically important difference of pain ranking in the post-operative period has been found to be approximately 2.4 point reduction for individuals with moderate severity pain[1,2]. Based upon the variance of pain reporting in prior studies, a standard deviation of 2.75 was assumed for the AUC over two days of NRS-11 scale surveys [1-4]. Incorporating a 1:1 randomization scheme, we will have 85% power to detect a 2.4 point difference with 25 patients per arm, for a total of 50 patients. However, not all patients who will be consented will ultimately undergo surgery (approximately 60% progress to surgery). We will therefore consent 85 patients for a goal of operating on 50 patients, and randomize only those who go into surgery. The study will stop once 50 patients undergo surgery. Approximately 150 to 250 microTESE procedures are conducted at our site annually. As a result, we plan to accrue and complete the study in 6 months (i.e. ~9 patients per month).

1. Cepeda MS, et al. What decline in pain intensity is meaningful to patients with acute pain? *Pain*. 2003;105(1-2):151-157.
2. Yeung J, et al. Liposomal Bupivacaine During Robotic Colpopexy and Posterior Repair: A Randomized Controlled Trial. *Obstetrics and gynecology*. 2018;131(1):39-46.
3. Karcioğlu O, et al. A systematic review of the pain scales in adults: Which to use? *The American journal of emergency medicine*. 2018.

4. Mehta A, et al. Perioperative celecoxib decreases opioid use in patients undergoing testicular surgery: a randomized, double-blind, placebo controlled trial. *J Urol*. 2013;190(5):1834-1838.

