#### **11.4.2 Analysis of Secondary Endpoints**

$AUC_{60\_hrs}$  will be similarly analyzed as the primary endpoint.

$AUC_{days1-7}$  will be similarly analyzed as the primary endpoint.

Total number of narcotics tablets required will be analyzed with a Poisson regression, with a relative rate estimated with appropriate 95% confidence intervals.

Time to rescue narcotic requirements will be assessed with Kaplan-Meier and cumulative incidence curves. A log rank test will be used to compare treatment and control arms. If no censoring occurs, mean time to rescue narcotics will be assessed with a t test and 95% confidence intervals obtained.

The percentage of patients who remain opiate free and the percentage of patients who are overall satisfied with pain control on day 7 will be analyzed with a chi-squared test, and a 95% confidence interval for the difference in proportions estimated.

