## 11.6 Reporting and Exclusions

**11.6.1 Evaluation of toxicity.** All patients will be evaluable for toxicity from the time of their first treatment with liposomal bupivacaine.

**11.6.2 Evaluation of response.** All patients included in the study will be assessed for response to treatment if they have received at least 1 treatments.

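### No rule scores a pain diary that ends before 48 hours: taken literally, the trapezoid gives a truncated AUC, and excluding the man instead erodes the stated 85% power

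*Combined protocol and SAP*

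**What the plan says.** - **Endpoint and scoring.** Section 1.1 sets the primary endpoint as the NRS-11 AUC over the first 48 hours. Section 11.1 gives the only scoring rule: "The area under the curve will be computed using the linear trapezoidal rule to interpolate between survey responses". Surveys come every 8 hours on days 1-2 and every 12 hours on days 3-7.
- **Test.** Section 11.4.1 specifies a two-sample t-test allowing for unequal variances at two-sided 0.05, with a Mann-Whitney test if normality fails. Under Section 11.4.2 the 60-hour and 7-day AUCs "will be similarly analyzed as the primary endpoint".
- **Who counts.** Section 11.6.2: "All patients included in the study will be assessed for response to treatment if they have received at least 1 treatments".
- **Leaving the surveys.** Section 5.4: "Subjects may voluntarily withdrawal from the survey-portion of the study at anytime without consequences to their subsequent care". Section 10.1 relies on prompting: "To ensure maximum compliance, subjects will be prompted with a text message to their mobile phone".
- **Sample size.** Section 11.2: "we will have 85% power to detect a 2.4 point difference with 25 patients per arm". It raises 50 to 85 consented men because about 60% reach surgery, and stops at 50 operated.
- **End of study.** The Endpoints row of the Protocol Summary instead ends the study when 50 men have had surgery and completed the surveys and follow-up. Section 7.3 orders 25 vials of study drug.

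No section gives an imputation, carry-forward, time-averaging or minimum-diary rule.

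**The concern.** The plan allows men to stop answering and keeps them evaluable, but leaves their primary endpoint value undefined. Gaps inside a diary are covered, as is a missed 48 h survey followed by a later answer. The gap is the diary with no answer at or after 48 h.

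Followed to the letter, the rule sums the area up to the last answer and stops, so a man who quits at 24 h appears to have had less pain than he did. Leaving him out avoids that, but sits badly with Section 11.6.2 and removes him from the 25 per arm. Carry-forward, time-averaging and imputation are not excluded either, but none is stated. At stake are the size of the estimated benefit, the power and, if stopping differs strongly between arms, the type I error. The scoring could also be chosen after the data are seen. The secondary AUCs inherit the gap, and their longer diaries give more time to stop.

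**Working it through.** **1. The plan's own power.** Inputs from Section 11.2: difference 2.4, SD 2.75, 25 per arm, two-sided 0.05. Noncentrality = (2.4/2.75) × √(25/2) = 3.09 on 48 df, giving power of 85.6%. The stated 85% reproduces if all 50 men contribute an AUC. Solving for 85% gives 24.6 per arm, so there is almost no reserve.

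**2. If short diaries are excluded.** The same formula gives 84.1% at 24 per arm, 80.7% at 22 and 76.7% at 20. The consent allowance does not help: 50/0.60 = 83.3, so 85 is used up by men who never reach surgery.

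**3. If short diaries are truncated, one man.** Constant pain 4 over 48 h: 4 × 48 = 192 point-hours. Last answer at 24 h: 4 × 24 = 96. The loss of 96/48 = 2 points of time-averaged pain is close to the 2.4-point target. For the 60 h AUC with a last answer at 48 h: 192 instead of 240 (-20%).

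**4. If short diaries are truncated, the arm difference.** Assumptions, none of them in the documents: surveys at 0, 8, ..., 48 h; stoppers' last answer equally likely at 16, 24, 32 or 40 h (20 h lost on average); control pain flat at 5 or falling from 7 to 3; treated pain 2.4 lower throughout. SD 2.75 is taken on time-averaged pain, so the true difference is 2.4 × 48 = 115.2 point-hours.

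Mean area lost per stopper:
- flat pain: control 5 × 20 = 100; treated 2.6 × 20 = 52
- falling pain: control (138.7 + 96 + 58.7 + 26.7)/4 = 80; treated 80 - 2.4 × 20 = 32

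Expected difference = 115.2 - (control rate × control loss) + (treated rate × treated loss). For 30/10 with flat pain: 115.2 - 30 + 5.2 = 90.4. Power and type I error come from simulation (25 per arm, within-man SD 1.5, Welch test, 20,000 trials per scenario).

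| Stopping %, control/treated | Expected difference, flat / falling | Power | Type I error |
|---|---|---|---|
| 0/0 | 115.2 / 115.2 | 85-86% | nominal 5% |
| 10/10 | 110.4 / 110.4 | 83-84% | about 5% |
| 20/10 | 100.4 / 102.4 | 77-79% | about 6% |
| 30/10 | 90.4 / 94.4 | 68-73% | 7-9% |
| 10/20 | 115.6 / 113.6 | 87% | about 6% |
| 10/30 | 120.8 / 116.8 | 89-91% | 7-9% |

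With no true effect, both arms lose 100 (or 80) per stopper, so the shift is the gap in rates times that loss: 8-10 point-hours at a 10-point gap and 16-20 at a 20-point gap, toward the arm that stops more. With the planned benefit, treated men must stop 100/52 = 1.9 to 80/32 = 2.5 times as often as control men before the estimate is inflated.

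**5. Sensitivity at 30/10.** First survey at 8 h instead of 0 h: power 62-68%, type I error 8-10%. SD 2.75 per survey (correlation 0.5, scores rounded and clipped to 0-11): power 84-88%, down from 98% with full diaries, and type I error 9-11%.

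**6. Stopping driven by pain.** Assumed hazard 15% per survey at a score of 7 or more, otherwise 1%; 16-18% of control and 9% of treated men stop. Truncation gives an estimate of 98-100 and power of 79-80%; type I error stays at about 5%.

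**7. Does the remedy work?** On data with a serial correlation pattern (0.3 + 0.7 × 0.6^lag, 10,000 trials), multiple imputation with 15 imputations gives power of 84-85%, type I error of 4.7-5.0% and an estimate of 115-116 at 10/10, 30/10 and 10/30. Under the pain-driven stopping of step 6 it gives 115 and 85%.

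**The case against.** Follow-up for the primary endpoint is two days, men are prompted by text, and stopping may be rare. That stands: if stopping is low and balanced, little is lost (83-84% power at 10/10). The documents give no rate, however, and prompting does not score a diary that still ends early.

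The Protocol Summary's end-of-study wording might be read as guaranteeing 50 finished diaries. It cannot carry that weight. Section 11.2 stops at 50 operated, Section 7.3 orders just enough vials for one 25-man arm, and no section provides for replacing a man who stops. Even with replacement, Section 11.6.2 keeps him evaluable with no defined AUC.

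A reader might infer that truncation always flatters the arm that stops more, or that a spurious benefit is likely. The first holds only with no true effect: at 10/20 under the planned benefit the expected estimate is 113.6-115.6 against 115.2. The second needs a large gap in stopping when the drug does nothing. Section 5 keeps patients blinded throughout, and the documents give no reason to expect such a gap.

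Nor are truncation and exclusion the only possible scorings. Both fit the text poorly: a 24 h sum is not a 48 h AUC, and exclusion conflicts with Section 11.6.2. A simpler rule could also close the gap. Carrying the last score forward held type I error near 5% at 30/10 and 10/30, though it shifts the difference by about 4 point-hours if pain falls (0.20 × 20). So imputation is a preferred choice and not the only defensible one.

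**Conclusion.** The point holds as a missing scoring rule for the primary endpoint, and the plan should be changed. The certain part is narrow: the stated method adds no area after the last answer, men may stop at will, all treated men are assessed, and the 85% power needs essentially all 25 diaries per arm.

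The size is not known in advance. The truncation figures rest on assumed stopping rates, pain profiles and survey times, and on reading SD 2.75 as time-averaged pain; other assumptions widen the 30/10 result to 62-88% power and up to 11% type I error. With a true benefit, truncation understates it unless treated men stop roughly two or more times as often as control men. The documents do not support saying that the trial is underpowered or its type I error inflated as it stands; they support saying that the plan does not protect against either. The truncation and exclusion figures are alternatives and must not be added.

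Section 1.2 equates 108 hours with 7 days, which is 168 hours. That is a separate point.

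**What to change.** State the following in Section 11.4 before unblinding:

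1. Truncated sums are not used for a diary with no answer at or after 48 h.
2. The planned Welch test is kept, on AUCs completed to 48 h by prespecified multiple imputation. Alternatively, the AUC difference is estimated from a likelihood-based repeated-measures model (arm by time) on all observed 0-48 h scores, as the trapezoid-weighted contrast of time-point means.
3. One missing-not-at-random sensitivity analysis is added.
4. The same approach applies to the 60-hour and 7-day AUCs.
5. If the Mann-Whitney fallback stays, the plan says how it is applied to imputed data.

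In Section 11.2, state that the 85% power assumes 25 analysable diaries per arm. Reconcile the Protocol Summary's end-of-study wording with the stop at 50 operated and the 25 vials, and say whether men who stop are replaced.

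The cost is SAP wording, slightly more analysis work and a missing-at-random assumption, which the sensitivity analysis tests. The scoring rule itself needs no extra patients or surveys.

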## **11.2 Sample Size/Accrual Rate**

The minimal clinically important difference of pain ranking in the post-operative period has been found to be approximately 2.4 point reduction for individuals with moderate severity pain[1,2]. Based upon the variance of pain reporting in prior studies, a standard deviation of 2.75 was assumed for the AUC over two days of NRS-11 scale surveys [1-4]. Incorporating a 1:1 randomization scheme, we will have 85% power to detect a 2.4 point difference with 25 patients per arm, for a total of 50 patients. However, not all patients who will be consented will ultimately undergo surgery (approximately 60% progress to surgery). We will therefore consent 85 patients for a goal of operating on 50 patients, and randomize only those who go into surgery. The study will stop once 50 patients undergo surgery. Approximately 150 to 250 microTESE procedures are conducted at our site annually. As a result, we plan to accrue and complete the study in 6 months (i.e. ~9 patients per month).

1. Cepeda MS, et al. What decline in pain intensity is meaningful to patients with acute pain? *Pain*. 2003;105(1-2):151-157.
2. Yeung J, et al. Liposomal Bupivacaine During Robotic Colpopexy and Posterior Repair: A Randomized Controlled Trial. *Obstetrics and gynecology*. 2018;131(1):39-46.
3. Karcioğlu O, et al. A systematic review of the pain scales in adults: Which to use? *The American journal of emergency medicine*. 2018.

4. Mehta A, et al. Perioperative celecoxib decreases opioid use in patients undergoing testicular surgery: a randomized, double-blind, placebo controlled trial. *J Urol*. 2013;190(5):1834-1838.

### **11.3 Stratification Factors**

Not applicable

### **11.4 Analysis of Endpoints**

#### **11.4.1 Analysis of Primary Endpoints**

Area-under-the-curve of the NRS-11 in days 1 and 2 ( $AUC_{days1-2}$ ) will be compared in treatment vs control groups using a two-sample t-test allowing for unequal variances, with a two-sided alpha of 0.05. A 95% confidence interval for the difference in  $AUC_{days1-2}$  between arms will be estimated along with estimate and confidence intervals of average  $AUC_{days1-2}$  within each arm. If significant deviations from normality are observed in  $AUC_{days1-2}$ , a non-parametric Mann-Whitney test will be used instead.

#### **11.4.2 Analysis of Secondary Endpoints**

$AUC_{60\_hrs}$  will be similarly analyzed as the primary endpoint.

$AUC_{days1-7}$  will be similarly analyzed as the primary endpoint.

Total number of narcotics tablets required will be analyzed with a Poisson regression, with a relative rate estimated with appropriate 95% confidence intervals.

Time to rescue narcotic requirements will be assessed with Kaplan-Meier and cumulative incidence curves. A log rank test will be used to compare treatment and control arms. If no censoring occurs, mean time to rescue narcotics will be assessed with a t test and 95% confidence intervals obtained.

The percentage of patients who remain opiate free and the percentage of patients who are overall satisfied with pain control on day 7 will be analyzed with a chi-squared test, and a 95% confidence interval for the difference in proportions estimated.

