##### **Post-operative recovery: week 1**

Study participants will complete online surveys generated from RedCap x 7 days. The survey will be administered every 8 hours in days 1-2, and every 12 hours in days 3-7. The surveys will ask the patients to rank their current pain (NRS-11), pain control satisfaction, and record the number of narcotic tablets required.

During the standard of care post-op call, the nurse will ask and record complications and also address patient questions.

Post-op visit (2-3 weeks post-op):

The post-op clinic visit allows for a routine wound check and a discussion of results. The subject will have an opportunity to ask questions regarding the surgery, should any debriefing be required.

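### Time to first rescue narcotic gets an effect estimate with a confidence interval only if nobody is censored, so even one opiate-free man leaves only curves and a p-value

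*Combined protocol and SAP*

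**What the plan says.** Section 11.4.2 sets out the analysis of this endpoint in three sentences. The description is: "Time to rescue narcotic requirements will be assessed with Kaplan-Meier and cumulative incidence curves". The comparison is: "A log rank test will be used to compare treatment and control arms". The estimate is conditional: "If no censoring occurs, mean time to rescue narcotics will be assessed with a t test and 95% confidence intervals obtained". The Protocol Summary, Section 1.2 and Section 11.1 name the endpoint but add no effect measure. No hazard ratio, difference in medians or restricted mean appears anywhere in the documents.

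Section 1.2 also lists as a secondary endpoint: "The percentage of patients remaining opiate free by post-operative day 7". Section 11.4.2 gives that endpoint a chi-squared test, with "a 95% confidence interval for the difference in proportions estimated". The tablet count gets a Poisson regression "with a relative rate estimated with appropriate 95% confidence intervals". The two secondary AUC endpoints follow the primary analysis, which includes an interval for the difference between arms.

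On follow-up, Section 5 (week 1) says: "Study participants will complete online surveys generated from RedCap x 7 days". Section 5.4 adds: "Subjects may voluntarily withdrawal from the survey-portion of the study at anytime without consequences to their subsequent care".

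**The concern.** A man who takes no narcotic in the 7-day survey period has no first-use time. He is censored at the end of that period. A man who leaves the surveys before his first tablet is censored when he leaves. The only branch with an estimate and interval therefore requires that every man in both arms takes a narcotic within 7 days and that nobody drops out beforehand. In that situation the opiate-free endpoint would be 0% in both arms, with nothing to compare. By planning to test that percentage, the protocol allows for the censoring that removes the estimate.

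What would be lost is the size of the effect on timing. A log-rank p-value does not say how many hours the study drug adds before the first narcotic, or how precisely 25 men per arm can show it. Every other secondary endpoint in Section 11.4.2 has an interval whatever the data look like; this one does not. A measure chosen after seeing the curves would be post hoc.

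**Working it through.** **The plan's own figures.** None is stated for this endpoint. The sample size comes from Section 11.2: 25 per arm, 50 in total, for 85% power on the primary endpoint. That figure reproduces. The noncentrality is 2.4 / (2.75 × √(2/25)) = 3.09, which gives 85.6% by the noncentral t distribution with 48 degrees of freedom and 87.0% by the normal approximation. Nothing below changes it.

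**Step 1: how likely is the no-censoring branch?** It needs zero opiate-free men among 50. If each man independently has probability p of being opiate-free at day 7, the chance is (1 − p)^50. The documents give no value for p, so a range is assumed.

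| Assumed p, both arms | Expected opiate-free men, 50p | Chance of none, (1 − p)^50 |
|---|---|---|
| 1% | 0.5 | 60.5% |
| 2% | 1.0 | 36.4% |
| 5% | 2.5 | 7.7% |
| 10% | 5.0 | 0.5% |
| 20% | 10.0 | 0.001% |

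If opiate-free men occurred only in the intervention arm, at 10%, the chance would be 0.90^25 = 7.2%. Having no opiate-free man is necessary but not sufficient, because withdrawal from the surveys before first use also censors. All these figures are therefore upper limits.

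**Step 2: what the plan yields if anyone is censored.** It yields two survival curves, two cumulative incidence curves and one p-value. Medians can be read off the curves, but no between-arm contrast and no interval is specified.

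**Step 3: does one measure cover both cases?** The restricted mean over 0 to 168 h (7 × 24) is the area under the Kaplan-Meier curve from 0 to 168 h. If every first use is observed within 168 h, the Kaplan-Meier curve is the empirical survival curve and the area under it is the ordinary sample mean. The difference in restricted means then equals the difference in means that the conditional sentence asks for. If some men are opiate-free through day 7, each contributes 168 h and the estimate is still defined.

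**Step 4: what do the data allow?** Section 9.1 has each survey ask for tablets taken since the previous one. Section 10.1 spaces surveys 8 h apart on days 1 and 2 and 12 h apart on days 3 to 7, which is 48/8 + 120/12 = 6 + 10 = 16 surveys. First use is thus known only to lie between two surveys. If it is dated to the survey that reports it, each time is late by up to 8 h early on and up to 12 h later.

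**The case against.** The strongest reply is that narcotic use is not left without effect sizes. The difference in opiate-free proportions is the day-7 contrast of the same process and has an interval, the tablet count has a relative rate with an interval, and the Kaplan-Meier curves give medians within each arm. This is correct and limits the damage. None of these, however, measures the delay to first use, which is what this endpoint is for.

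It can also be said that heavy censoring is only an inference, since no opiate-free rate is given. That stands. At an assumed 1% the no-censoring branch would be more likely than not to apply, before withdrawals are counted. The argument rests on a rate of a few per cent or more.

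A reader might go further and infer that, without censoring, the plan discards the log-rank test for a weaker t test. The documents do not support that. The log-rank sentence carries no condition, and the t-test sentence does not say that it replaces anything. Where the plan does substitute one test for another, as with the Mann-Whitney test in Section 11.4.1, it says so. Nor is the t test weaker in general: which test has more power depends on the distribution of first-use times, which the documents do not describe. All that remains is that two p-values could exist for one endpoint, with no statement of which leads.

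Finally, a hazard ratio or a difference in medians would also fill the gap. That is fair. The restricted mean is preferred because it carries the plan's own choice, mean time, into the censored case.

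**Conclusion.** The point holds as a gap in one secondary analysis. The sole between-arm estimate for time to first rescue narcotic depends on a condition that probably fails: the chance of no opiate-free man in 50 is 36% at an assumed 2% rate, 7.7% at 5% and 0.5% at 10%, and withdrawals lower it further. These figures assume independent men and a common rate in both arms, and the rates are assumptions. When the condition fails, the plan gives no estimate of the delay. The primary analysis and the sample size are untouched.

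**What to change.** In Section 11.4.2, replace the conditional t-test sentence with wording to this effect:

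> The log-rank test is the single test for this endpoint, whether or not censoring occurs. The effect estimate is the difference between arms in restricted mean time to first rescue narcotic over 0 to 168 h after surgery, with a 95% confidence interval.

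Three details should go with it:

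- **Timing rule.** State one rule for dating first use within the 8 or 12 h survey interval, such as the time of the survey that first reports a tablet, and apply it identically in both arms.
- **Horizon.** State 168 h explicitly, because Section 1.2 equates 7 days with 108 hours while 7 × 24 = 168.
- **Withdrawal.** State that men who leave the surveys before first use are censored at their last completed survey, and that this assumes leaving is unrelated to later narcotic need.

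The cost is a few lines of SAP text and standard software, with no new data and no change to the surveys. The small downside is that the interval timing makes the estimate somewhat coarse; that limitation is already in the data and should be acknowledged when the result is reported.
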